#### **6.4. Visit Windows**

In order to adapt to changes in subjects going to the investigator’s office due to COVID-19, visit windows will be applied to incorporate visits that are reported as unscheduled visits or are out of protocol specified visit window once subjects were able to return to the investigator’s office. Visit windowing will be applied for all analyses results of eye examinations. Examples of applicable eye exams are cycloplegic autorefractometry and, tonometry intraocular pressure.

There are two sets of visit windows that will be applied. A narrower set of visit windows to be used in any appropriate analyses of the PP Set and a broad set of visit windows for all other appropriate analyses.

The day included for a visit is provided in Table 1 and Table 2 below.

**Table 1: Visit Window Schedule (except for analysis of PPS)**

Visit	Scheduled Visit Day	Visit Window
Baseline	Day 1	≤ Day 1
Month 6	Day 182	Day 2- Day 273
Month 12	Day 365	Day 274 – Day 456
Month 18	Day 548	Day 457 – Day 639
Month 24	Day 731	Day 640 – Day 822
Month 30	Day 913	Day 823 – Day 1004
Month 36	Day 1096	Day 1005 – Day 1187
Month 42	Day 1278	Day 1188 – Day 1369
Month 48	Day 1461	≥ Day 1370

This document is confidential.

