**Table 2: Visit Window Schedule (for analysis of PPS)**

Visit	Scheduled Visit Day	Visit Window (±28day except Month 36 visit, ±42 days for Month 36)
Baseline	Day 1	≤ Day 1
Month 6	Day 182	Day 154 - Day 210
Month 12	Day 365	Day 337 – Day 393
Month 18	Day 548	Day 520 – Day 576
Month 24	Day 731	Day 703 – Day 759
Month 30	Day 913	Day 885 – Day 941
Month 36	Day 1096	Day 1068 – Day 1124
Month 42	Day 1278	Day 1250 – Day 1306
Month 48	Day 1461	Day 1419 – Day 1503

In case 2 or more visits occur within a visit window, the closest visit to the scheduled visit will be used for summaries and analysis. If 2 visits are equidistant from the scheduled visit, then the later visit will be used.

Stage 1 is scheduled to run from Baseline until the Month 36 visit. Stage 1 will end when the subject leaves the study or completes their Month 36 visit, whichever is earlier. Stage 2 will begin on the day of first dose after re-randomization.

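### Visit windows in SAP 6.4 ignore stage, so a late end-of-Stage-1 refraction can be labelled Month 42 and a refraction taken after re-randomisation can be labelled Month 36

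*SAP*

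**What the plan says.** SAP 6.4 introduces the windows because of COVID-19: "visit windows will be applied to incorporate visits that are reported as unscheduled visits or are out of protocol specified visit window". Their scope is wide: "Visit windowing will be applied for all analyses results of eye examinations", with cycloplegic autorefraction given as an example. Table 1, used for everything except the per-protocol analyses, counts all windows from Day 1. Month 36 is scheduled on Day 1096 with window "Day 1005 – Day 1187", Month 42 on Day 1278 with window "Day 1188 – Day 1369", and Month 48 on Day 1461 with a window open from Day 1370. When several visits share a window, "the closest visit to the scheduled visit will be used for summaries and analysis", and a tie goes to the later visit.

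The text after Table 2 defines the stages by events, with no day limit: "Stage 1 will end when the subject leaves the study or completes their Month 36 visit, whichever is earlier", and "Stage 2 will begin on the day of first dose after re-randomization". SAP 6.2 makes the latest result before Stage 2 medication, namely the Month 36 result, the Stage 2 baseline. SAP 3.8 and the protocol's Month 36 procedures put refraction before re-randomisation. SAP 8.1.1 analyses Months 6 to 36 as observed, without imputation.

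**The concern.** The windows carry no condition on stage, nominal visit, re-randomisation date or first Stage 2 dose. A refraction from a late Month 36 visit is the end of Stage 1 and the Stage 2 baseline by the event rules, but Month 42 by Table 1, and the SAP does not say which prevails. The stated purpose is to recover visits that "are out of protocol specified visit window once subjects were able to return", yet the literal rule takes a measured Month 36 outcome away from the child who came back more than 91 days late. SAP 8.1.4 plans no further sensitivity analysis for COVID-related missing data. The tipping-point categories are framed around subjects who terminate before Month 36, which a late completer has not done.

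The opposite error is also open. Unscheduled visits are windowed in, and nothing stops one that falls after re-randomisation from being selected as Month 36. Every vehicle child moves to atropine in Stage 2 (SAP 3.6.2), so such a value could enter the vehicle arm's primary endpoint on active drug.

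**Working it through.** **Inputs.** Scheduled days 913, 1096, 1278 and 1461, the windows, and the closest-visit and tie rules: SAP 6.4. Responder rates 0.25 and 0.07, with 136 and 91 evaluable: SAP 3.5.1. Protocol visit tolerance of ±2 weeks: synopsis, Study Procedures.

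**1. Reproduce Table 1.** The boundaries are midpoints of consecutive scheduled days.
- (913 + 1096)/2 = 1004.5, so Month 36 starts on Day 1005.
- (1096 + 1278)/2 = 1187, so Month 36 ends on Day 1187.
- (1278 + 1461)/2 = 1369.5, so Month 42 ends on Day 1369.

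All three match the table.

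**2. Lateness and label.** The last Month 36 day is 1187 − 1096 = 91 days late. Month 42 covers 1188 − 1096 = 92 to 1369 − 1096 = 273 days late. From 274 days late the label is Month 48.

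**3. One late visit under both sets of rules.** Take a Month 36 visit on Day 1200, 104 days late.
- Event rules (6.2 and the text after Table 2): end of Stage 1 and Stage 2 baseline.
- Table 1: Month 42.

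If both are applied, the change from Stage 2 baseline at Month 42 is that reading minus itself, which is zero.

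**4. The reverse case.** If the Month 36 visit is k days before Day 1096, a later refraction up to Day 1096 + k replaces it, because ties go to the later visit. With k = 14 the visit is on Day 1082, and any refraction up to Day 1110 would replace it. One on Day 1100 is 4 days from Day 1096 against 14. If the Month 36 visit is on or after Day 1096, a later refraction is farther away and cannot replace it.

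**5. Later Stage 2 visits, after a Day 1200 visit.**
- Assumption A, visits scheduled from the late visit: 1200 + 182 = Day 1382 and 1200 + 365 = Day 1565. Both fall in Month 48. Distances from Day 1461 are 79 and 104, so the true Month 42 result is kept as Month 48 and the true Month 48 result is dropped.
- Assumption B, visits kept on the original calendar, Days 1278 and 1461: the closest-visit rule prefers Day 1278 to Day 1200 for Month 42 (0 against 78 days), and Month 48 is labelled correctly.

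**6. Size in the primary contrast.** Planned evaluable subjects are 136 + 91 = 227. The rate of late visits is not given. Assuming 1% to 5%: 227 × 0.01 = 2.3 and 227 × 0.05 = 11.4, so about 2 to 11 subjects. Exact power of the two-sided Fisher test, by enumeration:

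| Assumed loss, both arms | n (0.02% / vehicle) | Power |
|---|---|---|
| 0% | 136 / 91 | 95.6% (plan states 95%) |
| 2% | 133 / 89 | 95.2% |
| 5% | 129 / 86 | 94.6% |
| 10% | 122 / 82 | 93.0% |

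For 0.01% against vehicle (91 per arm) power is 90.1% with no loss and 88.2% at 5% loss. These figures use the plan's subject-level sample-size test, not the eye-level mixed model. They speak to precision, not to any bias from omitting late attenders.

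**The case against.** The strongest reply is that an upper day limit is a reasonable choice. The endpoint is cumulative progression below 0.5 D, and a refraction several months late covers a longer interval and leans towards non-response. The window already allows 91 days against a protocol tolerance of two weeks. The SAP treats COVID-related gaps as missing at random, and the mixed model keeps the child's Month 6 to 30 results. This stands: it is a good reason to leave Days 1005 to 1187 as the primary window. It does not justify calling a reading taken before any Stage 2 dose a Stage 2 outcome.

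SAP 6.2 anchors the Stage 2 baseline to dosing, so the late reading does keep that role. That is correct, but it leaves the Month 42 label in place as well.

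The reverse error is narrow. With a Month 36 visit inside ±2 weeks, the intruding refraction must come within 28 days of it, while the next scheduled refraction is about six months away. It therefore needs an unscheduled visit at which refraction is measured. It should be rare, but a rule that permits it for the primary endpoint is easily closed.

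A programmer might window within stage unprompted. The SAP does not say so.

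Three stronger readings are tempting, and the documents do not support them. A reader might apply the rate to about 318 completers (436 × 0.73), but that figure spans all three arms and the primary contrast uses two. A reader might infer that the rebound summaries are generally corrupted, but the loss of the true Month 48 result needs Assumption A, and those outputs are descriptive. A reader might conclude that the child drops out of the primary analysis, but only the Month 36 observation is lost, and only if no other refraction lies in the window.

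**Conclusion.** The point holds as a defect in the labelling rule. Followed literally, Table 1 labels an end-of-Stage-1 refraction on Days 1188 to 1369 as Month 42, and the closest-visit rule allows a refraction after re-randomisation to stand as Month 36. Nothing found elsewhere in the two documents prevents either.

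The effect on power is small on any plausible assumption: about 2 to 11 of 227 outcomes at an assumed 1% to 5%, and about one percentage point at the upper end. The true frequency is unknown. The case for change rests on contradictory labels, the possible selective loss of late attenders, and the possibility of on-atropine values in the vehicle arm, rather than on lost power. The documents do not show that the primary result would be materially biased.

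**What to change.** Window within stage, by adding to SAP 6.4:

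1. No refraction after the first Stage 2 dose may be labelled Month 36.
2. No refraction before the first Stage 2 dose may be labelled Month 42 or Month 48.
3. The Month 42 and Month 48 windows are counted from the date of the first Stage 2 dose.
4. Days 1005 to 1187 remain the primary Month 36 window. A sensitivity analysis counts the late end-of-Stage-1 refraction as Month 36. For subjects who do not enter Stage 2, it uses their EOS Month 36 refraction if taken on or after Day 1005, so that early-termination examinations are not counted.

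Because the rules turn on the first Stage 2 dose date, SAP 6.2 (Stage 2 medication starts the day after the Month 36 visit) and the protocol's e-diary text (dosing recorded from the same evening) must be reconciled. The Month 36 refraction precedes the dose under either.

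The cost is SAP wording and programming, plus longer follow-up for the few late visits in the sensitivity run. The change is best made before the Stage 1 unblinding in SAP 11; if made later, it should be labelled as such. Reporting the number of end-of-Stage-1 refractions after Day 1187 by arm would replace the assumed rate.

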**Table 2: Visit Window Schedule (for analysis of PPS)**

Visit	Scheduled Visit Day	Visit Window (±28day except Month 36 visit, ±42 days for Month 36)
Baseline	Day 1	≤ Day 1
Month 6	Day 182	Day 154 - Day 210
Month 12	Day 365	Day 337 – Day 393
Month 18	Day 548	Day 520 – Day 576
Month 24	Day 731	Day 703 – Day 759
Month 30	Day 913	Day 885 – Day 941
Month 36	Day 1096	Day 1068 – Day 1124
Month 42	Day 1278	Day 1250 – Day 1306
Month 48	Day 1461	Day 1419 – Day 1503

In case 2 or more visits occur within a visit window, the closest visit to the scheduled visit will be used for summaries and analysis. If 2 visits are equidistant from the scheduled visit, then the later visit will be used.

Stage 1 is scheduled to run from Baseline until the Month 36 visit. Stage 1 will end when the subject leaves the study or completes their Month 36 visit, whichever is earlier. Stage 2 will begin on the day of first dose after re-randomization.

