## **Early Termination Visits**

Every effort should be made to keep subjects in the study and conduct all study visits as scheduled. If a subject is discontinued from study medication before the Month 48 visit, then all Month 48 (EOS) procedures should be performed at the visit the subject is discontinued.

If a subject is off study medication and is being followed for safety assessments then an EOS Month 36 visit should be completed, as these subjects will not continue on to Stage 2.

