#### Unscheduled visits

Unscheduled visits may occur at the Investigator's discretion to address any possible issues the subject may experience that are of concern to the subject or parent/guardian (e.g., blurry vision, pain, redness in one or both eyes).

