#### **9.8. Dilated Fundus Examination**

A dilated fundus examination is performed at Baseline and the Month 12, 24, 36, and 48 visits. Assessments of optic nerve head, macula, peripheral retina, iris, and vitreous will be provided for each eye individually.

Findings at each visit will be summarized by stage, visit and treatment group using descriptive statistics.

Dilated fundus examination results will be provided in subject data listings.

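### The closest-visit rule also covers safety eye exams, and no by-arm eye-exam table uses every post-baseline exam

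*SAP*

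**What the plan says.** SAP 6.4 sets the scope broadly: "Visit windowing will be applied for all analyses results of eye examinations". Its examples include a safety measure: "Examples of applicable eye exams are cycloplegic autorefractometry and, tonometry intraocular pressure". The stated purpose is inclusive: "visit windows will be applied to incorporate visits that are reported as unscheduled visits", prompted by missed and late visits during COVID-19. Table 1 governs everything except per-protocol analyses, so it governs the Safety Set tables. Its windows are about six months wide; Month 12, for example, is "Day 274 – Day 456". The selection rule is printed after both window tables and is not limited to either: if a window holds two or more visits, "the closest visit to the scheduled visit will be used for summaries and analysis", with ties going to the later visit.

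SAP 9.5, 9.6 and 9.9 summarise acuity, pupil size and IOP as observed value and change at each visit. SAP 9.7 and 9.8 summarise slit-lamp and fundus findings at each visit. The Index of Tables (14.3.4.1) lists one table per exam per stage and nothing else. SAP 6.1 makes the minimum and maximum part of the summary for eye-level continuous variables.

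The protocol synopsis leaves unscheduled visits to the investigator's discretion, for problems such as "e.g., blurry vision, pain, redness in one or both eyes". For a child who stops study drug before Month 48, "all Month 48 (EOS) procedures should be performed at the visit the subject is discontinued"; that set includes a fundus exam. On the routine schedule, "A dilated fundus examination is performed at Baseline and the Month 12, 24, 36, and 48 visits".

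**The concern.** For efficacy, one visit per window is an ordinary way to get one value per child per time point. For safety exams the same rule has a side effect. Visits made because an eye was blurred, painful or red are off-schedule by nature, so in a six-month window they usually lie further from the target day than the routine visit. An IOP, acuity or corneal finding recorded there would then be missing from the table meant to display it, and the displayed extremes would come from the retained visits only.

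Fundus exams raise a second, separate question. A fundus exam done because a child stopped drug can fall in a Month 6, 18 or 30 window, where no fundus exam is scheduled, and the SAP does not say where it is tabulated. SAP section 9 names the ophthalmic assessments as a basis for judging safety separately from adverse events, so these tables should reflect all the exams collected.

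**Working it through.** **Inputs.** Scheduled days and windows: SAP Table 1. Routine visit tolerance of ±2 weeks: protocol synopsis, Study Procedures. Fundus schedule: SAP 9.8. Stage 1 drop-out of 27% (about 10% per year): protocol synopsis.

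**1. Reproducing the plan's figures.** Table 1 cuts at midpoints between scheduled days: (182 + 365)/2 = 273.5, and Month 6 ends on Day 273; (365 + 548)/2 = 456.5, and Month 12 ends on Day 456. The other boundaries match too. The windows leave no gaps, so every post-baseline exam falls in one. Drop-out: 1 − 0.9³ = 27.1%, as stated.

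**2. One example.** An exam on Day 240 is in the Month 6 window (Day 2–273), at distance 240 − 182 = 58 days. A routine exam within ±14 days of Day 182 (Day 168–196) always beats it. The Day 240 exam is used only if the routine exam was missed or lay no nearer to Day 182.

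**3. General case.** Let the routine visit be j days from target. An unscheduled exam wins on 2j − 1 strictly closer days, plus one tie day if the routine visit was early.
- j = 0: it wins on 0 days.
- j = 14: it wins on at most 28 days. 28/183 = 15.3% (Months 12, 18, 24, 36); 28/182 = 15.4% (Month 30); 28/272 = 10.3% (Month 6).
- Average over offsets −14 to +14: Σ(4j − 1) for j = 1 to 14 is 406 days; 406/29 = 14.0 days. 14/183 = 7.7%; 14/272 = 5.1%.

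So about 85 to 100% of such exams are left out, assuming the routine visit took place within ±14 days and the unscheduled exam is equally likely on any day of the window. If the routine visit was missed, the unscheduled exam is kept.

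**4. Windows with no scheduled fundus exam, Stage 1.** Month 6: 272 days; Month 18 (Day 457–639): 183; Month 30 (Day 823–1004): 182. Total 637.
- Over all Stage 1 windows (Day 2–1187, 1,186 days): 637/1,186 = 53.7%.
- Over days before the scheduled Month 36 visit (Day 2–1095, 1,094 days): 637/1,094 = 58.2%.

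These are shares of days. The share of discontinuation exams depends on when children stop, which the documents do not give:

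| Assumed timing of stopping | Share in Month 6, 18 or 30 windows |
|---|---|
| Uniform, Day 2–1095 | 58% |
| Constant 10% per year | 59% |
| Constant 30% per year | 63% |
| Rising linearly with time | 51% |
| Only at 3-monthly visits | 55–64% |
| Only at 6-monthly visits | 60% |
| Only at annual visits | 0% |

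**5. What the closest-visit rule itself removes.** A discontinuation fundus exam after an on-target annual exam in the same window loses to it: Day 366–456 and Day 732–822, 91 + 91 = 182 days; 182/1,094 = 17% under uniform timing. If Month 6, 18 and 30 rows are displayed, this 17% is the Stage 1 loss. It takes no account of a later annual exam in the same window, which could displace an earlier discontinuation exam.

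**6. Stage 2, uniform over Day 1097–1460 (364 days).** The Month 42 window (Day 1188–1369) has no scheduled fundus exam: 182/364 = 50%. A further 91/364 = 25% (Day 1097–1187) shares the Month 36 window with an on-target Month 36 exam and loses to it.

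**The case against.** The best reply is that the SAP already has other routes. The treatment-emergent adverse-event tables in SAP 9.3 are by arm and not windowed by visit. They cover ocular events by severity, relationship, withdrawal and drug discontinuation, and listings keep all relevant data. This stands, and it defeats one tempting inference: that these exams disappear from every by-arm safety summary. They do not, if the finding is reported as an on-treatment event. What remains is that those tables hold no IOP, acuity or pupil values, depend on the site reporting an event, and stop at the last dose date of the stage. Listings do not compare arms.

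Second, the windows were written to bring unscheduled visits in. They do so when the routine visit was missed or lay further from target; otherwise the rule works the other way.

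Third, a reader might infer that over half of discontinuation fundus exams are lost, or even multiply 27% of 483 children (130) by 54% to get about 70. The documents do not support either. SAP 9.8 refers to findings at each visit and does not suppress Month 6, 18 or 30 rows. Drop-out is not an examined discontinuation: a child lost to follow-up may have no exam, and a child off drug is expected back for annual visits, where a persisting finding can still be seen. Most of that gap also comes from yearly exams meeting half-yearly windows, not from the closest-visit rule.

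Fourth, the protocol synopsis prescribes no exam set for unscheduled visits and gives no frequency, so how many values are at stake is unknown. Nor do the documents show that retained values are usually the resolved ones.

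**Conclusion.** The point holds for the eye-exam tables. SAP 6.4 reaches the safety exams, and SAP 9.5 to 9.9 contain no summary that uses every post-baseline exam. Where the routine visit was nearer the target day, an unscheduled or discontinuation exam in the same window is not tabulated. For unscheduled exams that is about 85 to 100% of those sharing a window with an on-time routine visit, under the timing assumption stated. The tabulated minimum and maximum need not be the true extremes, and the tables can understate on-study abnormalities.

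For fundus exams, windows with no scheduled exam cover about 54 to 58% of Stage 1 days. The share of discontinuation exams affected depends on unstated timing and on whether those rows are displayed; no count follows from the documents.

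A reader might go on to conclude that the comparison between arms is biased towards no harm. That is not shown: selection depends only on date, the same rule applies in every masked arm, and no between-arm effect can be calculated. The primary efficacy test is not affected by this point. It is a modest but worthwhile gap in the safety reporting.

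**What to change.** Keep the closest-visit rule for efficacy and for the by-visit safety rows. In SAP 6.4 and 9.5 to 9.9, add for each stage and arm:
- a worst post-baseline summary for acuity, IOP and pupil size;
- a summary of any new post-baseline abnormality for slit lamp and fundus.

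Both should use all scheduled, unscheduled and discontinuation exams of that stage, whatever their window. In SAP 9.8, state where a fundus exam outside the annual schedule is tabulated.

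The cost is a short SAP paragraph and an extra block of rows in the existing tables, using exams already recorded. One drawback needs handling: an arm with more unscheduled visits has more chances to record an extreme value, so show the number of exams per arm beside these summaries.

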#### **6.5. Pooling of Centres**

This section is not applicable because centre/country is not included in the statistical model.

#### **6.6. Subgroups**

Subjects are randomized based on two stratifications. The first stratification is by age (subjects < 9 years; subjects ≥ 9 years); the second is by refractive error (less myopic: SER -0.50 to -3.00 D; more myopic: one or more eyes with SER -3.01 to -6.00 D). The primary and secondary analyses will be repeated for each stratification.

Additional subgroup exploratory analyses will be performed differences between select demographic variables (Asian versus non-Asian; dark irides versus light irides; female versus male) and change from baseline in SER at Month 12, Month 24, and Month 36.

This document is confidential.

## 7. Demographic, Other Baseline Characteristics and Medication

### 7.1. Subject Disposition and Withdrawals

Subject disposition will be presented for all subjects, which include the following:

- Number of subjects enrolled
- Number of screened and reason for screen failure
- Number (%) of subjects randomized for Stage 1
- Number (%) of subjects re-randomized for Stage 2

Among the randomized subjects, the following will be summarized

- Number (%) of subjects in the Stage 1 Safety Set
- Number (%) of subjects in the Stage 1 Intent-to-Treat Set
- Number (%) of subjects in the Stage 1 Modified Intent-to-Treat Set
- Number (%) of subjects in the Stage 1 Per-Protocol Set
- Number (%) of subjects in the Stage 1 Modified Per-Protocol Set
- Number (%) of subjects who completed the Stage 1
- Number (%) of subjects who discontinued treatment in Stage 1 and their reason
- Number (%) of subjects who discontinued study prematurely in Stage 1 and their reason
- Number (%) of subjects who continuing the study into Stage 2
- Number (%) of subjects in the Stage 2 Safety Set
- Number (%) of subjects in the Stage 2 Intent-to-Treat Set
- Number (%) of subjects in the Stage 2 Modified Intent-to-Treat Set
- Number (%) of subjects in the Stage 2 Per-Protocol Set
- Number (%) of subjects in the Stage 2 Modified Per-Protocol Set
- Number (%) of subjects who completed the study (Stage 2)
- Number (%) of subjects who discontinued treatment in Stage 2 and their reason
- Number (%) of subjects who discontinued study prematurely in Stage 2 and their reason

A separate by-subject listing of subject disposition and withdrawal will also be provided. Subjects who screen failed will be listed along with the date and reason for the screen failure.

This document is confidential.

Randomized subjects not included in an analysis set and their reason for exclusion will be summarized and listed.

